- Health care resource utilization and cost inputs were used from published observational studies that were published up to 10 years ago. Revising these estimates with updated RWE could impact the drugs' cost-effectiveness.

The objectives of this observational RWE study are focused on addressing these uncertainties and generating updated cost-effectiveness model inputs. The following research objectives will be addressed:

Primary Objective. Describe baseline demographic characteristics, attack rates, and attack-related medical service utilization among initiators of one of the three treatments for long-term prophylaxis use (Takhzyro, Haegarda, or Cinryze).

- What is the HAE baseline attack rate per month (stratified by severity) in the six months pre-initiation?
- Where is on-demand treatment for acute attacks administered? What is the distribution of specific drugs? How many prescriptions do patients receive?
- For patients with severe attacks, what percent end up hospitalized, and within these patients, what is the utilization of procedures such as cricothyrotomy/tracheotomy, intubation, and artificial respiration?
- What are the costs associated with medical utilization during the acute attack?

Exploratory Objective: Explore attack rates and utilization following long-term prophylaxis initiation.

- What is the severe attack rate per month, post-initiation?
- What percent of patients are attack-free during the follow up period?

- What are the utilization patterns of the prophylactic medications, post initiation?
- What percent of patients receive less frequent dosing for Takhzyro after six months attack free (in line with FDA recommendations)? Do any patients titrate down prior to six months?

5. Research methods

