5.1.1.2 Prophylaxis initiation cohort for evaluation

[figure not shown]
Patients will be eligible to enter the cohort on initiation of Takhzyro, Haegarda, or Cinryze as a prophylactic treatment during October 10, 2008 through October 3rd, 2019 (Figure 1). October 2008 was selected as the start of the study period based on the approval date for Cinryze, the earliest of the medications to be approved. Clinical experts confirmed that 2008 reflects the current treatment paradigm of medications targeting the BK pathway and that all new treatments after 2008 reflect a continual shift away from inferior anabolic androgen therapies. The study period was also selected to maximize sample size for this rare disease.

New use will be defined as no use of Takhzyro or Haegarda, during the 180 days prior (washout period), and no use of Cinryze as a prophylactic treatment during this 180-day washout period. Because Cinryze is used for both acute attacks (off label) and prophylaxis, patients will be excluded based on evidence of prophylactic use of Cinryze (see definition in Annex 2) during the 180 days prior to cohort entry and will be required to have continuous enrollment and evidence of recurring use during the 90 days following cohort entry. Patients receiving other prophylactic treatments (see Annex 1) during the baseline period will also be excluded. Each patient will be included only once, on the first qualifying event. Patients will be required to have at least 180 days of enrollment prior to cohort entry to obtain baseline attack rates.

Using this cohort, we will evaluate baseline outcomes. Patients' demographic characteristics will be assessed at cohort entry. Patients' attack rates, and attack-related medical service utilization and costs will be evaluated.

Note: HAE does not have specific ICD9/10 diagnostic codes. We used initiation of HAE specific treatment to identify patients of interest (i.e., patients with HAE). The method of using HAE treatments to identify HAE patients has been used widely in the literature (Tachdjian 2020, Banerji 2020, [Vande Walle 2018](#)).¹⁻³ In addition, there is no indication that HAE treatments are used off-label for non-HAE patients.

Figure 1: Prophylaxis initiation cohort study design diagram

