5.1.1.3 Follow-up cohort for evaluating the exploratory research objective

The goal of the post-initiation exploratory analysis is to evaluate the frequency of attacks after initiation of prophylactic therapy, understand utilization, and determine how many months patients were attack free after initiation. This analysis will not directly influence the cost-effectiveness model; however, there is value in exploring these patient-relevant outcomes in real-world data.

The follow-up cohort will be derived from the baseline cohort. In addition to the baseline cohort inclusion criteria, all patients will be required to have a minimum of 90 days eligibility in the follow-up period. As in the baseline cohort, patients initiating Cinryze will be further required to have recurring use during the 90 days following cohort entry to confirm prophylactic use. Patients will be censored upon maximum follow-up of 365 days, disenrollment, the end of data (March 31st, 2020), or death, whichever comes first. Thus, patients will contribute a minimum of 3 months and a maximum of 1 year of follow-up time to the analysis. A one-year maximum follow-up was selected due to the recency of the Takhzyro approval (August 23rd, 2018).

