Pharmacy – on-demand drug utilization (# of scripts and total dose)			-	

Table 3: Descriptive analysis during follow-up (post initiation of prophylaxis)

Characteristic	Takhzyro initiators	Haegarda initiators	Cinryze initiators*	Notes
Mean age at initiation				
Female, %				

Distribution of severe attack free months				
Mean attack rate per month – severe-HAE specific- follow up period				
Proportion of patients with PDC >80%				
Switching- % patients switching to Takhzyro	N/A			
Switching- % patients switching to Haegarda		N/A		
Switching- % patients switching to Cinryze			N/A	

*Cinryze patients were required to be adherent to therapy in the 90 days post initiation to determine that they were taking Cinryze prophylactically (versus on-demand use). Takhzyro and Haegarda patients were not required to demonstrate adherence in the 90 days post initiation.

Table 4: Exploratory dose reduction outcomes

Characteristic	Takhzyro initiators	Notes
Percent of Takhzyro patients attack free for 6-month period		
Percent patients on every 4-week dosing for 6 months		
Percent of patients that titrated down to every 2-week dosing		

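### Table 3's percentage switching to Takhzyro counts initiators whose follow-up ended before Takhzyro was approved, so it is understated by an unknown amount

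*Protocol*

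**What the plan says.** Section 5.1.1.2 of the protocol gives all three drugs one entry window, 10 October 2008 to 3 October 2019, opening with the approval of Cinryze. Section 5.1.1.3 sets the end of follow-up: "Patients will be censored upon maximum follow-up of 365 days, disenrollment, the end of data (March 31st, 2020), or death, whichever comes first". It adds that "patients will contribute a minimum of 3 months and a maximum of 1 year of follow-up time to the analysis", and explains the cap: "A one-year maximum follow-up was selected due to the recency of the Takhzyro approval (August 23rd, 2018"). Switching drug does not end follow-up.

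Section 5.4.1.3 lists switching among the three drugs as something to explore, and calls the follow-up analysis descriptive because the sample is small. Table 3 in Annex 3 has one column of initiators per drug. Its rows include "Switching- % patients switching to Takhzyro", the matching rows for Haegarda and Cinryze, the proportion of patients with PDC above 80%, the distribution of months free of severe attacks, and a monthly severe attack rate. A footnote says that Cinryze patients had to be adherent for 90 days to show prophylactic use, and that "Takhzyro and Haegarda patients were not required to demonstrate adherence in the 90 days post initiation".

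Section 4 also asks: "What percent of patients are attack-free during the follow up period". It does not ask this by drug.

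**The concern.** A percentage switching to a drug is interpretable only among people who could have received that drug while observed. As the shell stands, the Takhzyro row in the Cinryze column divides by everyone who started Cinryze since 2008, although Takhzyro existed only in the last part of that window. Early starters enter as certain non-switchers. A reader could take a low figure as persistence on Cinryze when it partly reflects the calendar. Section 5.4.1.3, the limitations in 5.4.1.5 and the Table 3 footnote neither restrict the denominator nor mention this.

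Two lesser matters affect the same table. Follow-up length varies from 3 to 12 months and is cut by the end of data more often for Takhzyro. In addition, only Cinryze initiators are selected on 90 days of recurring use.

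**Working it through.** The protocol gives no by-drug figure to reproduce. The check is date arithmetic on its own dates, followed by illustrations whose assumptions are named.

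**Inputs.** Entry 10 October 2008 to 3 October 2019 (5.1.1.2). Cap of 365 days, end of data 31 March 2020, Takhzyro approval 23 August 2018 (5.1.1.3). Cinryze prophylaxis rule of at least 1,500 IU/week for at least 90 days (Annex 2). Cinryze prophylaxis schedule of 1,000 units every 3–4 days (Annex 1), used only to scale that rule.

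**1. Who can have an observed switch to Takhzyro.**
- Entry window: 4,010 days plus the first day = 4,011 days.
- 23 August 2018 minus 365 days = 23 August 2017. Starts from 10 October 2008 to 22 August 2017: 3,239 days, and 3,239 / 4,011 = 80.8%. Follow-up always ends before approval.
- Starts from 23 August 2017 to 22 August 2018: 365 days. Takhzyro is available for only part of follow-up (none beyond the approval date itself for the first of these days).
- Starts from 23 August 2018: 4,011 − 3,239 − 365 = 407 days. Takhzyro is available throughout.

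**2. Dilution, simple form.** Let f be the share of Cinryze initiators who started before 23 August 2017 and p the proportion switching among the rest. The table shows p × (1 − f). The protocol gives neither. With p = 30% and f from 50% to 80% (both assumed), it shows 0.30 × 0.50 = 15% down to 0.30 × 0.20 = 6%. The understatement is a factor of 1 / (1 − f), that is 2 to 5.

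**3. Dilution under uniform entry (assumed).** Take a constant switching hazard h once Takhzyro is approved, so the probability over t days at risk is 1 − exp(−h·t), averaged over entry days. About 13.7% of potential Cinryze follow-up time is then at risk.

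| True 12-month switching (assumed) | All Cinryze entry days | Entry on or after approval |
|---|---|---|
| 5% | 0.7% | 4.4% |
| 10% | 1.4% | 8.9% |
| 20% | 2.8% | 17.9% |
| 30% | 4.2% | 26.9% |

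The whole-window figure is about 6.5 times too low. That factor follows from uniform entry and is not an estimate for this database.

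**4. Follow-up length.** 31 March 2020 minus 365 days = 1 April 2019, so entry from 2 April to 3 October 2019 (185 days) cannot reach 365 days. That is 185 / 407 = 45% of Takhzyro entry days and 185 / 4,011 = 5% of Cinryze entry days. Under uniform entry the mean maximum follow-up is 323 against 361 days. At an assumed 0.1 severe attacks per month for both drugs, the expected percent attack-free over available follow-up is about 35% against 31%.

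**5. The Cinryze rule.** The Annex 1 schedule is 1,000 × 7/4 = 1,750 to 1,000 × 7/3 = 2,333 units per week. So 1,500 is 1,500/2,333 = 64% to 1,500/1,750 = 86% of it. For a patient who stops after day 90 and is followed for 365 days, this guarantees 0.643 × 90/365 = 16% to 0.857 × 90/365 = 21% coverage.

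**The case against.** The best defence is that Table 3 is exploratory. Section 5.4.1.3 calls it descriptive, no between-drug test is planned, and 5.1.1.3 says the follow-up analysis will not directly feed the cost-effectiveness model. Also, 81% of entry days need not be 81% of patients, since initiators may cluster late. Both statements are true. They limit the stakes and leave the size open, but a descriptive percentage still needs a denominator of people who could have the event.

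A reader might go further and infer that the by-drug columns mislead throughout. The documents do not support that.
- **Attack-free share.** One might infer that short follow-up flatters Takhzyro. Table 3 has no by-drug attack-free percentage, the illustrated gap is about 4 to 5 points, and a raw count of attack-free months works against Takhzyro. The attack rate is per month, so length alone does not bias it. The one-year cap is why the gap is small.
- **Cinryze adherence.** One might infer that the 90-day rule makes Cinryze look adherent whatever happens. The rule has a stated reason, off-label acute use, and the footnote discloses it. Its guaranteed coverage of 16–21% over a full year is far below a PDC of 80%. What remains is that the Cinryze column is not comparable with the others.
- **Attacks after a switch.** Keeping them with the first drug is a recognised choice in columns labelled by initiator, and not an error.

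**Conclusion.** The point holds for the switching rows. On the protocol's own dates, Cinryze starts on 3,239 of 4,011 entry days (81%) cannot produce an observed switch to Takhzyro, and the shell keeps those patients in the denominator. This needs no assumption. The same cut-off applies to any Haegarda initiator who started before 23 August 2017, and the same reasoning applies to Cinryze initiators and the row for switching to Haegarda. The Haegarda approval date is not in the document, so that part is not quantified.

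How far the percentage is understated depends on the calendar spread of initiators, which is not stated. The factors of 2 to 5 and about 6.5 are illustrations under the assumptions shown. Unequal follow-up is real but modest, and the Cinryze selection is a matter of labelling. Given the exploratory status, this is a correction worth making to one part of Table 3. It does not invalidate the follow-up analysis.

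**What to change.** In Table 3 and section 5.4.1.3:

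- **Switching rows (main change).** Restrict each row to initiators whose follow-up overlaps availability of the target drug. Start time at risk at the later of initiation and availability, and report cumulative incidence at a fixed horizon with the number at risk. State the availability date used for each drug.
- **Attack-free summaries (secondary).** Report attack-free months as a share of observed months. Report any percent attack-free by Kaplan-Meier at fixed times.
- **Footnote.** Extend the existing one to say that the PDC, switching and attack columns are not comparable across drugs, because only Cinryze is selected on 90 days of recurring use and the entry eras differ.
- **Optional sensitivity analyses.** A common day-91 landmark and an attack rate censored at switch could be added, but should not replace the planned results. A 90-day refill rule for all drugs as the main analysis would remove early discontinuers and spend follow-up time in a rare disease.

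The cost is smaller denominators, and so less precise figures, in the switching rows, plus a few lines of wording. No new data are needed.

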	Annex 3: Results Table Shells	27
	Annex 4: United Healthcare HAE Drug Coverage Policies	30

2. List of abbreviations

AEP	Action Evidence Platform®
ED	Emergency department
EHR	Electronic health records
FDA	Food and Drug Administration
HAE	Hereditary angioedema
HIPAA	Health Insurance Portability and Accountability Act
HTA	Health technology assessment
ICER	Institute for Clinical and Economic Review
IU	International unit
Kg	Kilogram
RCT	Randomized controlled trial
RWE	Real-world evidence
Rx	Prescriptions

3. Rationale and background

Drugs that receive accelerated approval through the FDA often have uncertainties in clinical and cost-effectiveness at time of launch and subsequent health technology assessment (HTA). ICER is piloting a process to reassess drugs, approved under accelerated pathways, 24 months after its initial assessment. The ICER reassessment will focus on using real-world evidence (RWE) to address uncertainties and update its initial clinical review and cost-effectiveness modeling.

A series of analyses using the Action Evidence Platform® (AEP) will be conducted within the Optum's de-identified Clinformatics® Data Mart Database to inform the RWE reassessment.

Results from this analysis and supplemented literature will be used by the University of Washington to provide updated inputs to the original HAE cost-effectiveness model.

4. Research questions and objectives

In the original [ICER HAE report](#), published in November 2018, a number of uncertainties were noted that could substantially impact the cost-effectiveness of the three therapies reviewed:

- Key cost-effectiveness model assumptions were based on data from RCTs (e.g., patients' baseline HAE attack rates), however, 'minor adjustments in key assumptions (e.g., frequency of attacks) could result in substantially different cost-effectiveness results.' How does real-world clinical practice align with the model assumptions derived from the RCTs?
- The FDA label for Takhzyro suggests that patients who remain attack-free for six months may be considered for less-frequent dosing (i.e., one dose every four weeks instead of every two weeks). However, the real-world proportion of patients who will switch to – and remain on – the less-frequent dose is unknown. Less frequent dosing could impact the incremental cost-effectiveness.

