5.1.1.4 Dose reduction cohort evaluating the exploratory research objective

[figure not shown]
The dose reduction exploratory cohort will only focus on patients initiating Takhzyro.

Patients will be eligible to enter the cohort on initiation of Takhzyro, during August 23, 2018 through July 5, 2019 (Figure 2). August 23, 2018 was selected as the start of the study period based on the approval date for Takhzyro. New use will be defined as no use of Takhzyro, during the 180 days prior to initiation (washout period). Each patient will be included only once, on the first qualifying event. Patients will be required to be continuously enrolled in the 180 days prior to

initiation and for at least 270 days post cohort entry. The FDA label for Takhzyro, states that patients whose attacks are well-controlled for six months should reduce dosing to every four weeks, thus the cohort will require a minimum of six months follow up plus 90 days to establish the new dosing regimen. To be included in the cohort, patients will be required to have dosing, on average, every two weeks during the 180 days post cohort entry.

Using the dose reduction cohort, we will determine the percent of patients that receive the less frequent dosing regimen after six months attack free.

Figure 2: Takhzyro dose reduction study diagram

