Annex 1: HAE drugs

Generic	Brand (Administration)	Acute Attack Dose	Long-Term Prophylaxis Dose	How Supplied
C1 Inhibitor, Human (plasma derived C1 inhibitor [pdC1INH])	Cinryze* (IV)	Adults† 1,000 units once. Additional 1,000 units IV if no improvement 60 minutes after first dose. (not studied in children)	Adults & Children ≥12 years 1,000 units every 3-4 days Max Dose: 2,500 units or 100 units/kg every 3 days Children (6-11 years) 500 units every 3-4 days Max Dose: 1,000 units every 3 days Short-Term Prophylaxis† (before a procedure) 20 units/kg or 1,000 units immediately prior to procedure	Cinryze 500 units Powder Vial Reconstitute with 5mL SWFI Concentration: 100 units/mL
	Haegarda* (SC)		Adults & Children ≥6 years 60 IU/kg twice weekly (every 3-4 days)	Haegarda 2000 IU Powder Vial Reconstitute with 4mL SWFI Concentration: 500 IU/mL Haegarda 3000 IU Powder Vial Reconstitute with 6mL SWFI Concentration: 500 IU/mL
	Berinert* (IV)	Adults & Children ≥6 year 20 IU/kg once		Berinert 500 IU Power Vial Reconstitute with 10mL SWFI Concentration: 50 IU/mL

Generic	Brand (Administration)	Acute Attack Dose	Long-Term Prophylaxis Dose	How Supplied
Lanadelumab	Takhzyro* (SC)		Adults & Children ≥12 years 300mg every 2 weeks. After 6 months, reduce to every 4-week dosing if patient well-controlled.	Takhzyro 300mg/2mL Solution Vial Concentration: 150mg/mL
C1 Esterase Inhibitor, Recombinant (recombinant human C1 inhibitor [rhC1INH])	Ruconest* (IV)	Adults & Children ≥13 years (non-laryngeal attacks) 50 IU/kg/dose Max Dose: 4,200 IU/dose; 8400 IU per 24 hours	Adults & Children ≥13 years† 50 IU/kg/dose once or twice weekly Max Dose: 4,200 IU/dose once or twice weekly Short-Term Prophylaxis† (before a procedure) 50 IU/kg or 1,000 units immediately prior to procedure	Ruconest 2100 IU Powder Vial Reconstitute with 14mL SWFI Concentration: 150 IU/mL
Ecallantide	Kalbitor* (SC)	Adults & Children ≥12 years 30mg once (administered as three injections of 10mg) Max Dose: 60mg in 24 hours		Kalbitor 10mg/mL Vial Solution for Injection (3 vials per package)
Icatibant	Firazyr (SC)	Adults 30mg once. Repeat administrations in 6-hour intervals. Max Dose: 90mg in 24 hours (EU Pediatric Dosing Weight Based)		Firazyr 30mg/3mL Solution Vial Icatibant 30mg/3mL Solution Prefilled Syringe
Berotrastat	Orladeyo* (Oral)		Adults & Children ≥12 years 150 mg once daily. Adjustment: 110mg once daily for hepatic impairment or GI reactions.	Orladeyo 110mg Capsule Orladeyo 150mg Capsule

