Android Methitest Testred Virilon (Methyltestosterone)	NDCs: 00187-0902-01 00115-1408-01 00187-0901-01 00115-7037-01	Clinical Pharmacology Database²⁰
Winstrol (Stanozolol)	NDCs: 0024-2253-04??	Clinical Pharmacology Database²⁰
Prophylactic use of Cinryze and Ruconest	Algorithm and code lists	Source
Cinryze prophylactic use	Cinryze is indicated for prophylaxis, but is used off-label for acute attacks. Prophylactic use will be defined as continuous refills of Cinryze averaging ≥ 1500 IU/week for ≥ 90 days.	Riedl 2018²²
Ruconest prophylactic use	Ruconest is indicated for on-demand use, but is used off-label for prophylaxis. Patients with Ruconest prophylactic use will be excluded from the cohort. Prophylaxis use will be defined as continuous refills of Ruconest averaging 50 IU/kg once weekly for 90 days.	Riedl 2018²²
every four-week	Used to determine if a dose reduction occurred.	

administration of Takhzyro	This will be measured over a 90-day follow-up period based on total dose <= 1200 mg over that period. The 1200 mg is based on three 300 mg injections plus one additional injection to account for potential variation in exact timing.	
Attack severity	Algorithm and code lists	Source
Severe	
ED visit with/without hospitalization, identified based on “Type of service” coded as inpatient or emergency room. Events identified as HAE-specific include at least one of the following diagnose (as a primary diagnosis for hospitalizations /or treatments indicative of an attack:
 
 € Codes often associated with HAE: ICD-9-CM 277.6 or ICD-10-CM D84.1 € Angioedema diagnosis: ICD-9-CM 995.1 or ICD-10-CM T78.3* € Administration of on-demand HAE treatment € Diagnosis of swelling, abdominal pain, or asphyxiation: 
 o ICD-9-CM 518.81, 518.84, 787.0*, 782.2, 789.0*, 786.02, 786.05, 786.1 o ICD-10-CM J96.0*, J96.2*, J96.9*, R06.0*, R06.1, R10.*, R11.*, R22.0*, R22.1, R19.0 	
UpToDate states severe attacks are treated in ED.²³
 
Tachdjian 2020¹
 
Zilberberg 2010²⁴
 
Longhurst & Bork, 2019

Non- severe attack	
Each dose of an on-demand therapy over two acute attack doses is considered an attack. The number of doses dispensed will be calculated from the quantity dispensed and recommended dose and
 
Any on-demand therapy administered outside an inpatient or emergency room setting will be considered a non-severe attack.
	
Utilization	Algorithm and code lists	Source

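### Table 4 misstates the Takhzyro step-down in rows 2 and 3, and the dose reduction cohort cannot answer the early step-down question without bias

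*Protocol*

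**What the plan says.** Section 4 of the protocol names "the real-world proportion of patients who will switch to" the less frequent Takhzyro dose, and stay on it, as an unknown that could affect incremental cost-effectiveness. It then sets two exploratory questions: "What percent of patients receive less frequent dosing for Takhzyro after six months attack free", and "Do any patients titrate down prior to six months".

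Section 5.1.1.4 builds a cohort for the first question: "we will determine the percent of patients that receive the less frequent dosing regimen after six months attack free". Entry needs at least 270 days of enrolment after initiation, and "patients will be required to have dosing, on average, every two weeks during the 180 days post cohort entry". No tolerance around that average is given.

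Annex 1 starts patients on 300 mg every two weeks and then says: "After 6 months, reduce to every 4-week dosing if patient well-controlled". The coverage policy in Annex 4 gives the same reduced schedule. Annex 2 defines four-weekly administration by the dose received: "This will be measured over a 90-day follow-up period based on total dose <= 1200 mg over that period".

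Table 4 in Annex 3 has three rows: the percentage attack free for a six-month period, the percentage on four-weekly dosing for six months, and "Percent of patients that titrated down to every 2-week dosing". It prints no denominators and has no row on step-down before six months.

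**The concern.** Row 3 makes the starting regimen the target of a reduction, so as printed it has no meaning. Row 2 attaches a six-month duration to a state that the protocol measures over 90 days.

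The second problem is one of design. Section 4 wants to know whether anyone steps down early, but the dose reduction cohort admits patients on the strength of not having done so. A count taken there would be pushed towards none, and a reader of the results could take that as evidence that early reduction does not happen in practice. Dosing frequency is one of the uncertainties that prompted the study, so the direction of that error matters even for an exploratory result.

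**Working it through.** **Row 3.** Section 4, section 5.1.1.4, Annex 1 and Annex 4 all give every four weeks as the reduced schedule. Over 90 days, two-weekly dosing is 90/14 = 6.4 doses (about 1,929 mg) and four-weekly dosing is 90/28 = 3.2 doses (about 964 mg). Only the second fits the 1,200 mg limit in Annex 2.

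**Row 2.** It can be read in two ways.
- As the first six months: ruled out by the entry condition.
- As the six months after day 180: this needs 180 + 180 = 360 days. Section 5.1.1.4 guarantees 270, and the last entry date, 5 July 2019, plus 270 days is 31 March 2020, the end of data. Only patients entering by 6 April 2019 could have 360 days. The Annex 2 measure covers 90 days.

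**Early step-down inside the cohort.** Inputs: 300 mg per dose (Annex 1), the 1,200 mg limit, which is 1,200/300 = 4 doses (Annex 2), and the 180-day dosing requirement (section 5.1.1.4). Assumption: doses are on schedule from day 0.

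Two-weekly doses on days 0, 14, ..., 168 make 13 doses, or 3,900 mg. Seven of them fall in days 0-89. A patient who meets the Annex 2 measure in days 91-180 therefore has at most 7 + 4 = 11 doses, or 3,300 mg. That is 3,300/3,900 = 85% of schedule, with a mean interval of 180/11 = 16.4 days.

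By the day of the last two-weekly dose, with 28-day gaps afterwards:

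| Last two-weekly dose (day) | Doses in 180 days | Mean interval (180/doses, days) | Dose in days 91-180 (mg) |
|---|---|---|---|
| 56 | 9 | 20.0 | 900 |
| 84 or 98 | 10 | 18.0 | 900 |
| 112 or 126 | 11 | 16.4 | 1,200 |
| 140 or 154 | 12 | 15.0 | 1,500 |
| no step-down | 13 | 13.8 | 1,800 |

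Because the protocol states no tolerance, the effect of the filter is shown as a range:
- No missing dose allowed: every early step-down in the table is excluded.
- One missing dose allowed (12 doses): those stepping down after day 140 or 154 stay in, but at 1,500 mg they do not meet the Annex 2 measure. Everyone who meets it is excluded.
- Two missing doses allowed (11 doses): only patients still on two-weekly dosing until about day 112 or later stay in.

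**The case against.** The row labels look like a transposition in an empty shell. The rest of the protocol is consistent about the reduced schedule, so an analyst would probably see the slip. That is fair, but swapping the labels is not a full repair: row 2 would then report two-weekly dosing for six months, which is about 100% by construction in a cohort selected on it.

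A reader might infer that the protocol has dropped the promised percentage stepping down among attack-free patients. The documents do not support that. Section 5.1.1.4 states this percentage correctly. Table 4 prints no denominators, so its rows could be meant as a sequence. The shells are also not a complete list of outputs: the Winsorized costs of section 5.4.1.2 and the sensitivity analyses of section 5.4.1.4 have no rows either. For the same reason, the lack of a row for early step-down does not by itself show that the result was abandoned.

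A reader might also infer that the study cannot answer the early step-down question at all. That goes too far as well. The follow-up cohort of section 5.1.1.3 includes Takhzyro initiators, needs only 90 days of follow-up and has no two-weekly dosing requirement for them. Section 5.1.1.4 does not claim the early question for its own cohort. What stands is that no section assigns the question to any cohort, and the one cohort built for dose reduction gives a biased answer.

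**Conclusion.** The point holds in this form. Rows 2 and 3 of Table 4 are wrong as printed, on the protocol's own text and without any assumption. Separately, an early step-down count within the dose reduction cohort would be biased towards none: with a tolerance of zero or one missing dose it would miss every patient who meets the Annex 2 measure by day 180. That range rests on on-schedule 300 mg doses and on a tolerance that the protocol does not give. The objective is exploratory and descriptive, and the main percentage is properly stated in the body text, so this is a minor-to-moderate correction, worth making before the tables are filled.

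**What to change.** (a) Replace rows 2 and 3 of Table 4 with one row: the percentage on four-weekly dosing (at most 1,200 mg over days 181-270) among patients attack free over days 1-180, with n and denominator. Do not relabel row 2 as two-weekly dosing.

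(b) State which cohort answers the early step-down question. Report it among all Takhzyro initiators with at least 180 days of follow-up, before the two-weekly dosing filter, for example from the follow-up cohort. Require sustained intervals of roughly 28 days per 300 mg dispensed, so that a single late or missed fill is not counted. Note beside the result that step-downs after about day 140 cannot be detected by a 90-day total within the first 180 days, since such patients still receive 1,500 mg in days 91-180.

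The cost is a shell edit and one extra count from the same data. The conditional row in (a) has a smaller denominator. In (b), some misclassification between poor adherence and deliberate titration will remain and should be stated.
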